1.0 Objectives

1.1 Study Objectives

Our long term goal is to understand the likely health effects of cigarette smokers switching to a Standardized Research E-Cig (SREC) and to assess the role of nicotine delivery on switching, acceptability and markers of health outcomes. The specific objective of this proposal is to recruit a cohort of 240 current exclusive daily cigarette smokers and to measure a comprehensive battery of health markers at baseline and at 3 and 6 weeks after attempting to switch completely to SRECs containing either zero or 58 mg/ml nicotine in a randomized double-blind, placebo-controlled design with the following three specific aims:

- **1.1.1** Aim 1: To characterize the short-term effects of attempting to switch from traditional cigarette smoking to a Standardized Research E-Cig from baseline to 6 weeks using a comprehensive battery of measures (e.g. carcinogen biomarker (NNAL), pulmonary function testing, Holter EKG, exhaled CO, and cotinine, BP etc.).
 - **1.1.1.1** Our hypothesis is that attempting to switch to a SREC will result in a reduction in markers of harms to health, as compared with the baseline (exclusive cigarette smoking) measures.
- **1.1.2** Aim 2: To compare the effects of switching to a standardized research electronic cigarette (SREC) with pods containing 58 mg/ml nicotine liquid versus 0 mg/ml nicotine liquid on smoking behavior and changes in health markers at 6 weeks post-switching.
 - **1.1.2.1** Our hypothesis is that nicotine-containing SRECs will facilitate switching from smoking more efficiently than zero nicotine SRECs and will result in a significantly greater improvement in markers of health risk, but will conversely result in higher ratings of dependence on the SREC (as compared to the zero nicotine SREC) at 6 weeks post-switching (after controlling for baseline measures).
 - **1.1.2.2** We also hypothesize that the nicotine-containing SRECs, (as compared with the zero nicotine SRECs, after controlling for baseline) will result in a lower total score for the withdrawal items on the MNWS and lower mean scores on ratings of cigarette craving, during the first week of the trial.

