1.2 Primary Study Endpoints

The primary endpoint for the study is creatinine-corrected urinary NNAL concentration at 6 weeks (after switching).

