3.3.1.2 General withdrawal criteria

Participants may be discontinued by the PI at any point during the study for any of the following reasons:

- **Missing their study visit window**: If a participant misses their study visit window, the participant will be considered for withdrawal from the study.
- **New pregnancy**: Participants who report a new pregnancy at any point during the study will be withdrawn.
- Suicide attempt: If at any time during the study it is discovered that a participant has made a suicide attempt, they will be withdrawn from the study.
- Cardiovascular disease (CVD) event requiring inpatient hospitalization: CVD typically includes MI (heart attack), PTCA (angioplasty/stenting), bypass surgery, stroke, peripheral vascular disease (arterial blockages in arms or legs leading to procedure or surgery). Less common CVD problems would be new cardiac arrhythmias (e.g., new atrial fibrillation) or new vavlular disease (e.g., mitral or aortic regurgitation).
- DVT/PE (deep vein thrombosis/pulmonary embolism, i.e., blood clots in the venous system) requiring inpatient hospitalization.

- Adverse events related to e-cig use: Adverse events will be monitored at every study visit.
- Worsening substance abuse in which the participant is behaving inappropriately at visits or demonstrates an inability to continue with the study.
- Any inpatient hospitalization or debilitation in which participation in the study could be detrimental to the recovery process. This will be self-reported by the participant and will be reviewed by the site PI and medical professional to determine whether continued participation in the study is appropriate (this could include recovery from a major surgery, worsening of psychiatric symptoms, etc.).
- Any situation where participant is not able to use their e-cig for a period of more than 2 weeks (e.g., incarceration or other similar situation) unless they report non-study product use by choice.
- **Participant choice**: Participants may choose to remove themselves from the study by informing the research team in writing at any point during the study. If they choose to remove themselves from the study, they will not receive any further contact from the study center.

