7.4.3 Method for Assigning Subject to Treatment Groups

Participants will be randomized to one of two conditions: a SREC with pods containing 0 mg/ml nicotine content (placebo) or a SREC with pods containing 58 mg/ml nicotine content (nicotine). Using a 1:1 allocation ratio, the randomization template was created by the study's unblinded statistician via blocked randomization. The Randomization Module in REDCap will assign each participant to a 6-digit alpha-numeric code upon randomization at Visit 1. This code is unique to each randomized participant and is accessible to all study personnel. This code provides a blinded reference which identifies the SREC-device kit to be assigned and associated with the pharmacy device distribution. The utilization of this alpha-numeric code allows study personnel to be blinded from the nicotine dose while simultaneously distributing the devices to the

participants. The master blinded randomization file links each alpha-numeric code to a randomized nicotine dose. This file does not exist in REDCap, is not stored on any shared accessible network drives, and is not accessible to any blinded study personnel (except in the event of an emergency situation that requires the breaking of the blind).

In the event that REDCap is down during a Visit 1 and a participant is ready to be randomized, the REDCap Randomization downtime procedure should be followed and implemented. This means that pharmacy will continue their list and no data will be entered into REDCap until participant can be randomized in the system.

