8.2 Sample size determination

We plan to randomize a total of 240 participants (120 in each dose group), and it is assumed that, although all efforts will be made to ensure 100% retention in the trial, as many as 30% of participants may drop-out after randomization. Thus, the effective sample size for this study could be as low as 84 per group, as the primary study endpoint is measured and collected at the last in-person study Visit 4.

Therefore, n=84 is the expected number of participants in each group to complete Visit 4 (e.g. complete the 'Switching Phase' of the study). It is expected that the NNAL levels in the nicotine-containing e-cigs group will be similar to results obtained by Goniewicz et al¹³ assuming a pre-treatment mean =225ng/ml creatinine (SD 165) vs. post-treatment 80 ng/ml creatinine (SD=69). The pre-treatment values of the placebo e-cigs group are expected to be similar to that of the nicotine-containing e-cigs group, as this measure occurs prior to randomization. The n=84 per group sample size should enable us to detect a post-treatment NNAL difference of 35 ng/ml creatinine or larger between groups (i.e., the placebo e-cigs group's post-treatment NNAL mean value be > 115), with at least 90% statistical power under 5% type 1 error.

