We will strive to minimize the number of missing values by rigorous follow-up with the study subjects. In spite of this, we still anticipate some missing values in the final datasets. Our basic tool to address this problem is multiple imputations. More specifically, if a variable is missing at V1, it will be imputed from the distribution of that variable of non-missing subjects. Due to the randomization at V1, non-missing subjects from both arms will be used for the distribution. For values missing at V3 (6 weeks after randomization), but non-missing at V2, the value collected at V2 will be carried forward in time via the LOCF (Last Observation Carried Forward) approach. For any instance where the participant remained in the trial, but did not provide data values at either post-randomization visit (V2 or V3), that case will be excluded from the analysis (modified ITT).

For some scenario, the missing values can be imputed by some reasonable assumptions. If a participant dropped out of the study prior to Visit 3 without providing Visit 2 data for the outcome, a 'worst-case-scenario' assumption will be made – assuming that the participant reverted back to exclusive smoking of cigarettes upon dropping out of the trial. Under this assumption, their Visit 2 baseline value will be carried forward to Visit 3. See the table below for a detailed outline of these methods:

V1	V2	V3	V` Baseline Result	V3 Endpoint Result	Mechanism of Missing		
+	+	+	Use directly Use directly		N/A		
+ + -			Lise directly	Impute V3 via LOCE from V2	Dropped out between V2 and V3		
	•	-			Missing V3 due to item non-response		
+	-	+	Use directly	Use directly	N/A		
-	+	+	Impute the V2 value from the overall sample distribution	Use directly	N/A		
			Use directly	Impute V3 via LOCF from V1	Dropped out between V1 and V2 Assume 'Worst-Case- Scenario'		
+	-	-	Excluded from Analysis (N	Dropped out between V2 and V3 Item Non-Response at V2			
			Excluded from Analysis (N	Completed the Switching Phase Missing V2 and V3 due to item non-response			
	Impute the V1 value		Impute the V1 value	Impute V2 via LOCE from V2	Dropped out between V2 and V3		
-	T	-	distribution		Missing V3 due to item non-response		
-	-	+	Impute the V1 value from the overall sample distribution	Use directly	N/A		
-	-	-	Excluded from Analysis (Modified ITT)				

Stratified Imputation Approach:

(+) = non-missing data(-) = missing data

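### Carrying baseline NNAL forward for early dropouts is not a worst case for the arm comparison, and the plan has no sensitivity analysis to show how far unequal early dropout drives the result

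*Combined protocol and SAP*

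**What the plan says.** Section 1.2 makes creatinine-corrected urinary NNAL at 6 weeks the primary endpoint. Section 8.3 (Aim 2) regresses the week-6 value on arm with adjustment for baseline.

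The missing-data part of section 8.3 names multiple imputation as the basic tool but gives early dropouts one fixed value. Someone who leaves before Visit 3 without Visit 2 outcome data is handled by "assuming that the participant reverted back to exclusive smoking of cigarettes upon dropping out of the trial", and the baseline value becomes the Visit 3 value. The text calls that value a Visit 2 baseline. The table carries Visit 1 forward, and section 8.3 defines baseline as Visit 1, so Visit 1 is used here. The rule is the same in both arms. No analysis varies it: the covariate-adjusted models and the abstainer subgroup address other questions.

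The Aim 2 text of section 8.3 restricts the modified intent-to-treat set to participants with outcome data at Visit 2 or Visit 3. Read alone, that leaves the same early dropouts out.

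On attrition, section 8.2 allows that "as many as 30% of participants may drop-out after randomization" and concludes that "the effective sample size for this study could be as low as 84 per group". Dropout is therefore planned as equal between arms, with no split into before and after Visit 2.

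**The concern.** An analysis presented as a worst case should work against the trial's hypothesis. This rule works against whichever arm loses more people early. If that arm is placebo, the error favours nicotine.

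More early dropout on placebo is plausible, although the plan does not state it. Section 1.1.2.2 predicts that the nicotine product "will result in a lower total score for the withdrawal items on the MNWS and lower mean scores on ratings of cigarette craving", and section 8.3 expects 40% abstainers on nicotine against 20% on placebo.

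Leaving the study is also not the same as relapse. Section 3.3.1.2 lets the investigator discontinue people for reasons such as pregnancy or hospitalisation, and also says: "If a participant misses their study visit window, the participant will be considered for withdrawal from the study". None of these shows a return to baseline smoking, and section 8.3 does not say whether such exits count as dropping out.

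At stake is whether a significant NNAL difference reflects lower exposure or unequal attendance. As written, nothing in the planned output would tell the two apart. The retention reports in section 10.7 are not split by arm.

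**Working it through.** **The plan's own figure.** 120 × 0.70 = 84 per arm. With SD 69, difference 35 and two-sided 5%, power = Φ(35 / (69 × √(2/84)) − 1.96) = 0.908. The stated power of at least 90% reproduces. It takes dropout as equal and gives imputed participants no role.

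**Inputs.** From section 8.2: 120 per arm; NNAL 225 (SD 165) before switching and 80 (SD 69) after; target difference 35, so a placebo mean of 115. From section 8.3: the imputation rule and the baseline-adjusted regression. Assumed, because the documents give none: early-dropout rates by arm, the Visit 1 to Visit 3 correlation, and the share of dropouts who return to baseline NNAL.

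**Shift in the estimate.** Each imputed value is on average 225 − 80 = 145 above the planned week-6 mean. With no true difference:

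shift = (early dropout on placebo − early dropout on nicotine) × 145

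| Gap (placebo minus nicotine) | Apparent benefit for nicotine |
|---|---|
| 5 points | 0.05 × 145 = 7.25 |
| 10 points | 0.10 × 145 = 14.5 |
| 15 points | 0.15 × 145 = 21.75 |
| 24 points | 0.24 × 145 = 34.8, about the whole target |

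If both arms truly sit at 115, the multiplier is 225 − 115 = 110, and a 10-point gap gives 11.0. If nicotine loses more people, the sign reverses. If early dropout is equal, no spurious difference arises, but a true 35 shrinks: 35 × 0.85 = 29.75 at 15% in each arm and 35 × 0.70 = 24.5 at 30%.

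**How much of the shift is bias.** If a share f of early dropouts (the same in both arms) really returned to baseline NNAL, their imputed values are about right. So bias = gap × 145 × (1 − f). For a 10-point gap this is 14.5 at f = 0, 14.5 × 0.5 = 7.25 at f = 0.5, 14.5 × 0.25 = 3.6 at f = 0.75, and 0 at f = 1.

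**Error rate at f = 0.** Simulation of 4,000 trials per setting: log-normal NNAL, correlation 0.5, 120 per arm, no true effect, dropout at random with the stated probability, baseline-adjusted regression.

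| Early dropout, nicotine vs placebo | Two-sided rejection, both arms at 80 | Both arms at 115 |
|---|---|---|
| 10% vs 15% | about 10% | 7–9% |
| 10% vs 20% | 23–25% | about 17% |
| 10% vs 25% | about 44% | 31–32% |

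Nearly all rejections favour nicotine. With equal early-dropout probability (10%, 15% or 30% in both arms) rejection is 5.0–5.5%. If the number of dropouts per arm is instead held exactly at the stated rate, the rates are lower: 5–7% at 10% vs 15% and 18–22% at 10% vs 20% over correlations 0.3 to 0.7 (these two in nicotine's favour, nominal 2.5%), and 1–2% in total when early dropout is equal at 15% or 30%. The shift is the same either way.

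An analysis of observed values only holds about 5%. That is because dropout was simulated as unrelated to NNAL, so it does not show that such an analysis is better here.

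**The case against.** A reader might infer that more dropout on placebo is enough by itself to produce a false benefit for nicotine. The documents do not support that. Falsity needs a second condition: that dropouts kept switched-level NNAL. People who leave because of craving are among the likeliest to be smoking again. Entrants were daily smokers, pods are supplied in limited numbers, and section 7.4.6.4 says the device cannot be used without study pods. If all early dropouts relapsed, the arm difference is a real effect of assignment. The rejection rates above are the f = 0 extreme. This stands.

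The imbalance is also assumed. Section 1.1.2.2 is about symptom scores, not attrition, and section 8.2 plans 84 and 84. The 30% covers all dropout, whereas only loss before Visit 2 data triggers this rule; later dropouts carry Visit 2 forward. This stands too, so the direction is conjecture.

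A reader might further infer that a missing-at-random analysis should replace the rule as primary. That does not follow. If dropouts relapsed, treating them like comparable stayers misses a real difference. One untestable assumption would replace another.

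Finally, the plan uses worst-case for an assumption about the participant and nowhere claims that it is conservative between arms. That is fair. The label still invites that reading, and no planned analysis would correct it.

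**Conclusion.** The concern holds conditionally. If the early-dropout row of the imputation table governs the primary NNAL analysis, carrying baseline forward in both arms is not conservative for the comparison. It moves the estimate by about 14.5 per 10-point gap in early dropout (about 41% of the 35 target, 14.5/35), against the arm that loses more people. Between none and all of that shift is bias, depending on how many dropouts returned to baseline NNAL, and the trial will not observe that. If the analysis-set wording governs instead, these participants are excluded and this mechanism does not arise.

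The figures rest on the section 8.2 means, on assumed dropout gaps, and for the rejection rates on f = 0 and a correlation of 0.5. They show what could happen, not what is expected. The defect is that the primary test could reject on unequal attendance with nothing planned to reveal it. This is a worthwhile, inexpensive strengthening of the plan and does not show the primary analysis to be invalid.

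**What to change.** 1. Reconcile the two parts of section 8.3, and state whether early dropouts enter the primary NNAL analysis and whether investigator withdrawals count as dropping out.
2. Baseline carried forward may stay primary if the sponsor prefers it. Describe it as assumed return to baseline smoking and drop the worst-case label.
3. Pre-specify two sensitivity analyses: (a) multiple imputation under missing at random; (b) an arm-specific tipping-point analysis, or baseline carried forward in the nicotine arm only with placebo dropouts multiply imputed.
4. Report early dropout by arm and reason beside the primary result.
5. Claim a robust NNAL benefit only if it survives (b) over a plausible range fixed in advance.

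The cost is SAP wording and two extra analyses, with no new data. The conclusion may become more qualified. The nicotine-only version of (b) is severe: at 10% early dropout on nicotine it moves the estimate 0.10 × 145 = 14.5 against nicotine, so a true 35 would read as 20.5. A tipping-point analysis over a stated range is therefore the more informative choice.

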9.0 Confidentiality, Privacy and Data Management

See the Research Data Plan Review Form.

9.1 Confidentiality

9.1.1 Identifiers associated with data and/or specimens See the Research Data Plan Review Form.

9.1.1.1 Use of Codes, Master List

See the Research Data Plan Review Form.

- **9.1.2** Storage of Data and/or Specimens See the Research Data Plan Review Form.
- 9.1.3 Access to Data and/or Specimens See the Research Data Plan Review Form.
- 9.1.4 Transferring Data and/or Specimens N/A
- **9.2 Subject Privacy** See the Research Data Plan Review Form.

10.0 Data and Safety Monitoring Plan

10.1 Periodic evaluation of data

The study coordinator and the PI will be responsible for the oversight of subject safety. Patients will be under medical supervision while in the study (i.e., by the medical monitor) and seen on an ongoing basis by our research staff who will document adverse events. The medical monitor ([name]) will assess adverse events and will consult with the pulmonologist on respiratory adverse events. The PI and/or the medical monitor will meet weekly with the study staff to review patient's progress and their experiences with the study products, including any adverse events. Entrance criteria will be reviewed following screening. Medical history will be reviewed by the study staff, and based on eligibility criteria, any questionable medical histories will be brought to the attention of the medical monitor for final inclusion determination prior to randomization. In a similar manner, contraindications for the treatment products and vital signs will be checked by study staff at each in person visit. The medical monitor will be available via phone for any consultations as necessary. In addition, the study coordinator/statistician will prepare a cumulative report of all data points listed below for the Data and Safety Monitoring Committee to review every 6 months after recruitment begins.

10.2 Data that are reviewed

The Data and Safety Monitoring Report will include:

- Accrual and retention
- Medical history and concomitant medications
- Adverse events and serious adverse events
- Protocol deviations/violations
- Misconduct
- Conflict of interest
- Participants' ability to achieve study requirements
- Changes in lung function via pulmonary function testing
- Changes in lung function via the Clinical COPD questionnaire

10.3 Method of collection of safety information

All data, including safety data, will be coded directly into REDCap case report forms during study visits and during phone contacts. Participant adverse events and serious adverse events will be assessed at each in-person study visit and phone call visit but can be reported at any time during the study.

10.4 Frequency of data collection

Safety data, including adverse events and serious adverse events will be collected at each in-person visit.

10.5 Individuals reviewing the data

The study coordinator and the PI will be responsible for the oversight of subject safety. The PI and the medical monitor will meet weekly with the study staff to review patient's progress and their experiences with the study products, including any adverse events. For more urgent and/or serious adverse events, the medical monitor will be available for consultation by phone. The medical monitor will then make any needed medical recommendations and a determination regarding whether the participant is able to continue with the study. For respiratory adverse events, the pulmonologist will be available for consultation. The DMSB will review the reports every 6 months.

10.6 Frequency of review of cumulative data

Safety data will be reviewed cumulatively based on recommendations from the DSMB. They will receive summary reports every six months and convene at least annually.

10.7 Statistical tests

There are no planned interim statistical analyses for this study. Statistical summaries and reports for all enrolled study participants will be generated for periodic DSMB Review. Reports will include summarized data and information pertaining to participant recruitment and accrual, study retention-dropout rate (withdrawals, lost to follow up, Switching Phase completion, Trial completion), (serious) adverse events, pulmonary function, and any other safety data requested by the DSMB (such as blood pressure, heart rate, weight, CO increases, etc.). The DSMB will meet to determine the desired format for the reports and the requested content (e.g. individual-level data, aggregate summary data, etc.). The data presented/reported will not be summarized by treatment group, thus allowing the reviews to occur in a blinded fashion for the DSMB, the PI, the study team, and the statisticians generating the reports.

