19.6 Unblinding Procedures

If an adverse event requires the subject to be unblinded, the unblinded study personnel will be able to provide that information as needed. Otherwise, participants will not be unblinded to their e-cig product allocation. The DSMB will begin by reviewing the protocol and establishing guidelines for data and safety monitoring including any additional procedures for unblinding of participants.

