19.7 Stopping Rules

There are no planned interim statistical analyses or stopping rule assessments for this study due to the low risk of the intervention. The DSMB will convene and notify the study team if they believe at any point, upon review of the safety data presented in the DSMB reports, that certain risks to subjects inflicted by continuing in the study outweigh the likely benefits of study completion. A brief report will be generated from each of the DSMB meetings for the study record and will be forwarded to the Institute's Institutional Review Board (IRB).

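### The default DSMB reports are pooled over both arms, and the plan does not say how or when the board would obtain a between-arm safety comparison

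*Combined protocol and SAP*

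**What the plan says.** All references are to the combined protocol and SAP.

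- **Report format.** Section 10.7 lets the DSMB settle the format and content of its reports, including individual-level data and any further safety data it asks for. The next sentence sets a limit: "The data presented/reported will not be summarized by treatment group". The stated purpose is blinding of the board itself, "thus allowing the reviews to occur in a blinded fashion for the DSMB", and equally of the PI, the study team and the statisticians who produce the reports.
- **The board's task.** Section 19.7 has the DSMB notify the study team if it believes that "certain risks to subjects inflicted by continuing in the study outweigh the likely benefits of study completion". It is to reach that view "upon review of the safety data presented in the DSMB reports". Sections 10.7 and 19.7 plan no interim analysis, and 19.7 plans no stopping-rule assessment.
- **Content and timing.** Section 10.2 lists accrual and retention, adverse and serious adverse events, and lung-function change among the reported items. Section 10.6 sets reports every six months and a meeting at least once a year.
- **Powers in reserve.** Section 19.6 has the DSMB begin by "establishing guidelines for data and safety monitoring including any additional procedures for unblinding of participants". It also provides: "If an adverse event requires the subject to be unblinded, the unblinded study personnel will be able to provide that information as needed". Section 10.8 lets the board develop stopping rules if it finds a problem.
- **Who holds the allocation.** Section 7.4.3 states that "the randomization template was created by the study's unblinded statistician". Section 7.4.5 counts the study statisticians among the unblinded; section 10.7 describes the statisticians generating the reports as blinded.

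**The concern.** The board is asked to weigh the risk of continuing, and the reports it is to use leave out the one comparison that randomization provides.

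That comparison matters here because harm could fall more heavily on either arm. Under section 7.4.1 the two pods share volume, propylene glycol and glycerin base, and flavor; nicotine, 58 versus 0 mg/ml, is the stated difference. Section 11.1.1 lists palpitations, abnormal heart rate and chest pain among e-cigarette side effects. Section 11.3 expects withdrawal symptoms, including depressed mood, in people who stop smoking. The plan gives no reference rate for any of these, so a pooled frequency has nothing to be compared with. Dropout, which section 8.2 allows to reach 30%, would also be seen only overall.

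At stake is an imbalance that builds up over several six-monthly reports and is noticed only when the blind is lifted after the last week-10 call (7.4.5).

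**Working it through.** **The plan's own figures.** The documents give no adverse-event rate and no monitoring threshold, so there is no safety figure to reproduce. The sample-size statement in section 8.2 does reproduce: 120 × 0.70 = 84 completers per arm, and with a difference of 35, an SD of 69 and two-sided 5% (sidedness assumed), power is 90.8% by the normal approximation and 90.5% by the t distribution. Nothing below changes it.

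**Inputs.** 120 participants per arm (8.2) and 1:1 allocation (7.4.3). All event counts and rates below are assumptions chosen for illustration.

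**Step 1: one pooled count, several arm splits.** With n per arm and m events in total, the probability of a events in one arm is C(n,a)·C(n,m−a)/C(2n,m). The two-sided Fisher p-value sums this over all splits no more probable than the one observed.

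| Per arm | Pooled report | Split | Rates by arm | Fisher p |
|---|---|---|---|---|
| 120 | 36/240 = 15% | 18 / 18 | 15% / 15% | 1.00 |
| 120 | 36/240 = 15% | 12 / 24 | 10% / 20% | 0.046 |
| 120 | 36/240 = 15% | 9 / 27 | 7.5% / 22.5% | 0.0018 |
| 120 | 24/240 = 10% | 12 / 12 | 10% / 10% | 1.00 |
| 120 | 24/240 = 10% | 6 / 18 | 5% / 15% | 0.016 |
| 120 | 24/240 = 10% | 4 / 20 | 3.3% / 16.7% | 0.0009 |
| 60 | 18/120 = 15% | 6 / 12 | 10% / 20% | 0.20 |

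For a given total, the board would receive the same report whatever the split. The last row is the 12/24 pattern at half enrolment, where even a table by arm would not be striking.

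**Step 2: what by-arm tables could show.** For true rates p₁ > p₂, power is the sum of Bin(a; n, p₁)·Bin(b; n, p₂) over all a > b with Fisher p < 0.05.

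| Assumed rates | 60 per arm | 120 per arm |
|---|---|---|
| 2% vs 10% | 28% | 68% |
| 5% vs 15% | 33% | 67% |
| 5% vs 20% | 63% | 94% |
| 10% vs 25% | 49% | 84% |

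These are single tests of one event type, used to gauge visibility; they are not a proposed stopping rule. A pooled table has no power for the contrast. It can show only a raised overall rate, and only against an outside reference that the plan does not supply.

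**Step 3: can the board get round the bar?** Section 10.7 gives it control of content and then excludes a summary by group; individual listings without arm still allow no comparison. Section 19.6 opens a route, but it speaks of unblinding participants, leaves the procedure unspecified and does not mention the bar. Unblinding for an adverse event (19.6) and stopping rules (10.8) come into play after something already looks wrong, and an arm imbalance is what pooled data do not show.

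**The case against.** A reader might infer that the board can never see a harm confined to one arm and cannot carry out its review. The documents do not support that. Section 19.6 gives the DSMB authority at the outset to add unblinding procedures and allows unblinding when an event requires it. Section 10.7 lets it ask for individual-level data, and section 10.8 lets it write stopping rules that will be followed. What is missing is the trigger, the procedure and a reconciliation with the bar.

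Nor is pooled review empty. Spirometry and blood pressure are measured at Visits 1, 2 and 3, so each participant serves as his or her own control. Worsening of lung function by 10% or more is recorded as an adverse event and goes to the medical monitor within five business days (7.2.2.7.7), and section 19.3 adds weekly causality review. Many of the risks in section 11.1 belong to e-cigarettes in general and would be expected in both arms; for these, pooling gives more data and a table by arm might look balanced.

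The illustration also has limits. Its counts are hypothetical, and at 120 per arm enrolment is complete and little exposure remains to prevent. Finally, blinded review is a deliberate choice, with its reason stated, in a six-week trial whose intervention the protocol calls low risk.

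All of this stands, and it narrows the point. It does not remove it: the individual-level reviews are not cumulative by arm, the reserve powers are mostly reactive, and the blinding of the PI and study team does not require the board to be blinded too.

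**Conclusion.** The point holds in limited form. The default DSMB reports exclude any between-arm safety comparison, section 19.7 bases the risk-benefit judgement on those reports, and the plan does not say how the board's power under section 19.6 fits with the bar in section 10.7. The board can still judge within-person change, serious individual events and harms common to both arms, and it has a route, though an unspecified one, to allocation data.

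That a pooled count carries no information about the arm contrast needs no assumption. How much would be gained by showing the arms rests on assumed rates: for the pairs examined, a single Fisher test has 28% to 63% power at 60 per arm and 67% to 94% at 120 per arm. This is a worthwhile, inexpensive improvement to safety oversight. It does not affect the validity of the primary analysis.

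**What to change.** 1. In section 10.7, replace the bar with a two-part report. The open report stays pooled. A closed report, for the DSMB only, shows adverse events, serious adverse events, retention, spirometry and vital signs by masked arm (A/B), with the key available to the board on request.
2. Assign the closed report to the unblinded randomization statistician of section 7.4.3. The PI, the study team and whoever prepares the open report remain blinded.
3. Reconcile section 7.4.5 with section 10.7 on which statisticians are unblinded. The proposal depends on this, since the two sections currently describe the statisticians differently.
4. In section 19.6, state that the DSMB's additional unblinding procedures include access to the closed report and the key, and cross-refer to sections 10.7 and 19.7.

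The cost is a second set of tables every six months and a written procedure for handling the closed report. With no interim efficacy test, there is no alpha to spend and no change to the 240 participants.
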